## 5. MILESTONES

The milestones for the study are presented in Table 2.

Each registry will be deemed to start data collection after the European Commission's (EC) final decision on the Article 20 for Janus kinase inhibitors (JAKi's) (i.e. 10 March 2023; for details, see Section 6) and identification of the first eligible filgotinib patient in the registry.

An interim study report will be provided with data including 24 months of data collection following the study start date; preparation of the interim report will take approximately 9 months. A full analysis will be performed with data including 48 months of data collection; the analyses and drafting of the full report will take approximately 12 months.

*Note*: SWIBREG will require additional time for linkage data to be available. Thus, the consolidated reports will be created once the last registry has provided its results.

The overall study period will therefore account for the timing of the start of the study, the data collection periods (including chart abstraction), data linkage, data management, data analysis, and submission of the consolidated interim and final report.

Milestone	Planned Date
Protocol submission (first version)	Within 18 months after European Commission (EC) approval of filgotinib for the treatment of UC (by 12- May-2023 at the latest)
Start of data collection	With the first patient identified per register after the EC decision date on Article 20 on JAKi's (i.e. after 10 March 2023)
End of interim data collection*	Q1 2027
End of data collection*	Q1 2029
Interim report submission (with 2 years of data)	End of interim data collection + 9 months (Q4 2027)
Registration in the EU PAS register	Within 4 months after protocol approval
Final study report submission (with 4 years of data)	End of data collection + 12 months (Q1 2030)

EU = European Union; PAS = post-authorization study; UC = ulcerative colitis

\* corresponds to the date at which the analytical dataset to perform the statistical analyses is completely available (this would be after chart abstraction in ENEIDA [won't be done for the interim report] and data linkage across the Swedish registers [usually linked data for a calendar year become available approximately 13 months after year-end, i.e. in January the year after next])

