## 8. **RESEARCH METHODS**

## 8.1. Study Design

This DUS is based on a non-interventional, post-authorization, prospective, multicountry, registry-based, longitudinal follow-up (cohort) design with secondary use of data collected from 3 European IBD registries. The registries to be used are: (i) the ENEIDA Register from Spain (ES), (ii) the ICC Register from the Netherlands (NL), and (iii) SWIBREG from Sweden (SWE). Data from the 3 European IBD registries may be enriched with additional (secondary) data collection information if needed and applicable. The study fulfills the criteria of a non-interventional PASS (category 3) in accordance with the commitment to the EMA and to the MHRA from the United Kingdom.

The study population will include up to 500 consecutive adult patients of any sex with UC and initiating treatment with filgotinib following implementation of the aRMMs after EC's final decision on Article 20 (decision date: 10 March 2023) per registry.

The observational period will be 4 years starting after the EC decision date on Article 20 (i.e. after 10 March 2023). It will include all follow-up time until dropout for the included patients.

Two reports will be generated: an interim report with 2 years of data collection (to be submitted within 9 months after end of interim data collection), and a final study report with 4 years of data collection (to be submitted within 12 months after end of data collection).

*Note*: The end of data collection, i.e. the timepoint by which the analytical dataset to perform the statistical analyses is completely available, is highly correlated with the process of chart abstraction (ENEIDA) or data linkage (SWIBREG). Thus, interim and final study reports will not be available within 9 and 12 months, respectively from the end of the observational periods.

In addition, in the ENEIDA registry, the set-up of ethics approvals, contracts and necessary activities (e.g. trainings) with all individual centers before chart abstraction can begin will likely take up to 2 years, based on prior experience in conducting similar PASS in this registry. It is important to keep this in mind for the scope of the interim report since it will be limited to information readily available in the ENEIDA registry (i.e. without supplementing its information with chart abstraction).

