# Figure 2 Estimated 95% Confidence Interval by Study Size and Underlying Proportion (Assuming a Binomial Distribution)

## 8.6. Data Management

## 8.6.1. ENEIDA (ES)

This study will involve analysis of secondary data from the ENEIDA registry, as described in Section 8.4. The automated data are maintained and managed by the ENEIDA registry in a password-protected MySQL database, which is maintained on a server in a secure facility. The investigator or qualified designee is responsible for verifying the accuracy of patient data as it is entered into the ENEIDA registry. All analyses will be conducted using SAS software.

This study involves chart review for all patients exposed to filgotinib identified in the automated data. Linkage between the automated record and the patient record will be based on the patient identification number and clinical site identifier.

Data will be accessed by Research Triangle Institute Health Solutions (RTI-HS) according to ENEIDA's standard practice. RTI-HS will log on to the ENEIDA secure server, download the data files, and store the data in a secure server in Barcelona with backups in the EU. Only selected RTI-HS personnel in Barcelona will have access to the data. Once the data are received,

RTI-HS will develop a data dictionary using SAS PROC CONTENTS. The data dictionary will document any data transformations applied to the received data sets to create the analytical datasets. The data dictionary will include variable names, formats, and any SAS code used to create derived variables from raw variables.

The transfers of data from ENEIDA may include data for patients who do not qualify for the analytic purposes of the present study. However, these data may be used to determine whether the analytic database is representative of the ENEIDA registry data in its totality. All data received from the registry will be covered by the IC signed by all patients at enrolment in ENEIDA. Chart abstraction will require patients to sign a study-specific IC to be able to obtain information of variables that are not part of the ENEIDA registry scope (see also Section 9.3.1). Data not used for the analysis will be filtered out at RTI-HS. Only data essential to the planned analyses will be retained in the analytic database.

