#### Follow-up

Among women starting filgotinib, the number and proportion who become pregnant during follow-up will be reported. Similarly, the number and proportion of patients who have a new

diagnosis of TB during follow-up, a serious acute infection, a diagnosis of viral hepatitis, concomitant treatment with other immunosuppressants, or who are administered a live attenuated vaccine will be reported. In patients with TB, or a serious infection identified during follow-up, it will be assessed whether treatment was stopped or interrupted after the diagnosis. The proportion of patients who have a test for lipids at around 12 weeks since initiation of filgotinib will be reported.

Should a VTE event occur, subsequent changes to filgotinib use will be reported (filgotinib treatment persistence or discontinuation).

Assessment of the filgotinib maintenance dose during follow-up will also be done in the subgroup of patients at high risk of MACE, VTE, or malignancy. In addition, the average daily dose during the maintenance period and the duration of use during the follow-up period will be reported.

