# 9.3. Informed Consent

### 9.3.1. ENEIDA (ES)

This non-interventional study will involve no administration of any therapeutic agent according to the study protocol; patients in ENEIDA are treated in the setting of usual clinical care. Patients whose data are included in ENEIDA previously consented to have their health information included in this database.

For the current study, some of the variables of interest extend beyond the field of UC and are not routinely collected in ENEIDA. As a consequence, a new IC will need to be obtained for this PASS for all patients that participate in the chart abstraction component of the study. If necessary, because of low enrolment in the chart abstraction component, patients for whom an IC cannot be obtained may still participate in the study addressing only those objectives that can be assessed using data collected in the registry.

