Long-time smoking (current or past) for > 10 years	no (if not available, might be in medical report)	no (but can be added)	yes (SWIBREG, but suboptimal coverage [approximately 57%])		
Hx of atherosclerotic CVD	no (might be in medical report)	yes (as part of medical history/comorbidity)	yes (NPR)		
Angina	no (might be in medical report)	yes (as part of medical history/comorbidity)	yes (NPR)		
Coronary heart disease	no (might be in medical report)	yes (as part of medical history/comorbidity)	yes (NPR)		
Myocardial infarction	no (might be in medical report)	yes (as part of medical history/comorbidity)	yes (NPR)		
Congestive heart failure	no (might be in medical report)	yes (as part of medical history/comorbidity)	yes (NPR)		
Stroke	no (might be in medical report)	yes (as part of medical history/comorbidity)	yes (NPR)		
Peripheral artery disease	no (might be in medical report)	yes (as part of medical history/comorbidity)	yes (NPR)		

Variable	Availability in individual registries yes/no (additional comments)				
	ENEIDA (ES)	ICC (NL)	SWIBREG (SE)		
Other CV risk factors		yes (as part of medical history/comorbidity)	yes (NPR)		
Diabetes mellitus (type 1 or 2)	yes (if not available, might be in medical report)	yes (as part of medical history/comorbidity)	yes (NPR)		
Hypertension	yes (if not available, might be in medical report)	yes (as part of medical history/comorbidity)	yes (NPR)		
Obesity/BMI	no (might be in medical report)	yes (as part of medical history/comorbidity)	yes (NPR)		
Current malignancy	yes (if not available, might be in medical report)	yes (as part of medical history/comorbidity)	yes (Cancer Register)		
Hx of malignancy	yes (if not available, might be in medical report)	yes (as part of medical history/comorbidity)	yes (Cancer Register)		
SmPC section 4.4: Special warnings and precautions for use: Immunosuppressive medicinal products					
Concomitant use of immunosuppressants/-modulators (e.g. ciclosporin, tacrolimus etc)	yes	yes	yes		
Concomitant use of advanced therapies (e.g. biologics [including TNF $\alpha$ - inhibitors], non-biologics [e.g. S1P receptor agonists)	yes	yes	yes		
Concomitant use of JAKi's other than filgotinib	yes	yes	yes		
SmPC section 4.4: Special warnings and precautions for use: Viral reactivation					
Viral hepatitis	yes	yes	yes (NPR)		

Variable	Availability in individual registries yes/no (additional comments)		
	ENEIDA (ES)	ICC (NL)	SWIBREG (SE)

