Dx date of viral hepatitis	Inconsistently (might be in medical report)	yes	yes (NPR)
Herpes zoster (HZ)	yes (if not available, might be in medical report)	yes	yes (NPR)
Dx date of HZ	Inconsistently (might be in medical report)	yes	yes (NPR)
Screening for TB	yes	no	yes (SmiNet)
Date of screening for TB	yes (possibly in ENEIDA or medical history)	no	yes (SmiNet)
Screening for HZ	yes	no	no
Date of screening for HZ	yes (possibly in ENEIDA or medical history)	no	no
Screening for viral hepatitis	yes	yes	no
Date of screening for viral hepatitis	yes	yes	no
SmPC section 4.4: Special warnings and precautions for use: Haematological abnormalities			
Laboratory measurement of ANC	no (might be in medical report)	no (only total leucocyte count, but it can be added)	yes (currently for <20%)
Date of measurement	no (might be in medical report)	yes (leucocyte count at baseline [week 0])	yes (currently for <20%)
Laboratory measurement of ALC	no (might be in medical report)	no (only total leucocyte count, but it can be added)	yes (currently for <20%)
Date of measurement	no (might be in medical report)		yes (currently for <20%)

Variable	Availability in individual registries yes/no (additional comments)		
	ENEIDA (ES)	ICC (NL)	SWIBREG (SE)
Laboratory measurement of Hb	no (might be in medical report)	yes	yes (currently for <20%)
Date of measurement	no (might be in medical report)	yes	yes (currently for <20%)
SmPC section 4.4: Special warnings and precautions for use: Vaccinations			
Use of live, attenuated vaccines	yes (if not available, might be in medical report)	no (but can be added)	no
Date of vaccine administration	yes		no
HZ vaccination	yes (if not available, might be in medical report)	no (but can be added)	no
Date of vaccine administration	yes		no
SmPC section 4.4: Special warnings and precautions for use: Venous thromboembolism (VTE)			
(Age 65+)	yes	yes	yes
Long-time smoking (current or past) for > 10 years	yes (if not available, might be in medical report)	no (but can be added)	yes (SWIBREG, but suboptimal coverage)
Hx of atherosclerotic CVD	no (might be in medical report)	yes (as part of medical history/comorbidity)	yes (NPR)
Angina	no (might be in medical report)	yes (as part of medical history/comorbidity)	yes (NPR)
Coronary heart disease	no (might be in medical report)	yes (as part of medical history/comorbidity)	yes (NPR)

Variable	Availability in individual registries yes/no (additional comments)		
	ENEIDA (ES)	ICC (NL)	SWIBREG (SE)

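### In ENEIDA, high-risk status rests on registry fields alone at the interim and on registry plus charts at the final report, so the Spanish high-risk proportion is understated at the interim and rises with the added source

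*Protocol*

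**What the plan says.** **Source at the interim.** Section 8.1 says of the interim report that "it will be limited to information readily available in the ENEIDA registry (i.e. without supplementing its information with chart abstraction". The footnote to the milestones table in Section 5 agrees: "this would be after chart abstraction in ENEIDA [won't be done for the interim report".

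**Source at the final report.** Section 8.6.1 states: "This study involves chart review for all patients exposed to filgotinib identified in the automated data". Abstraction needs a new study-specific consent. Under Section 9.3.1, if enrolment in the chart component is low, "patients for whom an IC cannot be obtained may still participate in the study addressing only those objectives that can be assessed using data collected" by ENEIDA itself.

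**Outputs.** The Abstract (Data Analysis) lists the proportion of patients at high risk of MACE, VTE, malignancy or infection. Section 8.7 (Follow-up) adds maintenance dose "in the subgroup of patients at high risk of MACE, VTE, or malignancy". Neither distinguishes interim from final.

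**Registry content.** In Annex 3 Table 5, ENEIDA is marked "no (might be in medical report") for every atherosclerotic CVD item, obesity/BMI, reduced mobility, recent hospitalization, clotting disorder, hormonal contraceptives and hormone replacement. Diabetes, hypertension, current and past malignancy, and previous VTE are marked "yes (if not available, might be in medical report"). Age 65+ is an unqualified yes. Long-time smoking is "no (if not available, might be in medical report") in the box-warning block but "yes (if not available, might be in medical report") in the VTE block.

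**Missing values.** Section 8.7.1.1 says that in ENEIDA a blank for a predefined variable is, in most instances, read as the condition being absent.

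**The concern.** A Spanish patient whose only risk factor is a past myocardial infarction or obesity cannot be recognised as high risk from registry fields. At the interim that patient falls outside the high-risk group, and at the final report the chart may bring the patient in. The label stays the same while its content changes.

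Use in patients with these risk factors is a stated objective (Section 7). Section 6 describes different maintenance posology for patients aged 65 or older or at higher risk, so group membership decides which recommendation a patient's dose is assessed against. The interim report is a regulatory deliverable (Q4 2027), and Section 10 sends aggregate data to periodic safety reports. Anyone who sets the interim and final Spanish figures side by side would see a rise that owes something to data source and nothing to prescribing.

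**Working it through.** **1. The plan's own precision figure.** Section 8.5 takes a 10% high-risk proportion with n = 300. SE = √(0.10 × 0.90 / 300) = 1.73%, and 10% ± 1.96 × 1.73% gives 6.6% to 13.4%, as stated. This serves as the yardstick.

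**2. Which components exist when (Table 5, ENEIDA).**

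| Component | Interim | Final |
|---|---|---|
| Age 65+ | registry | registry |
| Diabetes, hypertension, malignancy, previous VTE | registry | registry, topped up from charts |
| Long-time smoking | contradictory entries | registry or charts |
| Atherosclerotic CVD, obesity/BMI | none | charts, if consent |
| Reduced mobility, hospitalization, clotting disorder, hormone use | none | charts, if consent |

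Charts essentially add risk factors, so the proportion is pushed upward.

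**3. Size for the proportion.** Let P be the true high-risk share, s the share of high-risk patients found from registry fields, and c the chart coverage at the final report. The protocol gives none of these, so all are assumptions. P is held constant to isolate the source change.

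Interim = P × s. Final = P × (s + (1 − s) × c).

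| P | s | c | Interim | Final |
|---|---|---|---|---|
| 10% | 0.9 | 1 | 9.0% | 10.0% |
| 10% | 0.5 | 1 | 5.0% | 10.0% |
| 20% | 0.7 | 1 | 14.0% | 20.0% |
| 20% | 0.7 | 0.6 | 14.0% | 17.6% |
| 20% | 0.7 | 0.3 | 14.0% | 15.8% |
| 20% | 0.5 | 1 | 10.0% | 20.0% |
| 40% | 0.5 | 1 | 20.0% | 40.0% |

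Over P = 10% to 40%, s = 0.5 to 0.9 and c = 0.3 to 1, the rise runs from 0.3 points (P = 10%, s = 0.9, c = 0.3) to 20 points (P = 40%, s = 0.5, c = 1). That is 0.2 to 7.1 times the standard error of the final proportion at n = 300.

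**4. A component-based cross-check.** Assume 20% are high risk on registry fields, with independent chart-only factors. With CVD 5% and obesity 12%, the final figure is 1 − 0.80 × 0.95 × 0.88 = 33%. If long-time smoking (15%) is also chart-only, it is 1 − 0.80 × 0.95 × 0.88 × 0.85 = 43%. The Table 5 contradiction alone is worth about 10 points here. Low assumptions (2%, 5%, and smoking 5%) give 26% without smoking and 29% with it; high assumptions (6%, 18%, 25%) give 38% and 54%. These figures lean high: risk factors probably cluster, chart coverage is taken as complete, and the 20% base exceeds the 2% to 15% illustrated in Table 4.

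**5. Dosing in the subgroup.** Let a and b be the shares on a given maintenance dose among registry-identified and chart-only high-risk patients. With c = 1, the interim figure is a and the final is s × a + (1 − s) × b. With a = 60% and b = 40%, the interim is 60% and the final is 50%, 54% or 58% for s = 0.5, 0.7 or 0.9. With a = 40% and b = 60%, it moves from 40% up to 50%, 46% or 42%. If a = b it does not move. Table 5 also lets maintenance dose be topped up from charts, which is a second route to a change.

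**The case against.** The strongest reply is that the limit is disclosed. Section 8.1 ties it to the scope of the interim report, Sections 8.3.1 and 8.3.2 collect variables subject to registry availability, and Section 8.9 says many ENEIDA variables need extraction from medical records. Section 8.7 leaves detailed methods to an SAP that is not shown, and the protocol contains no operational high-risk algorithm. Nothing says outright that a Spanish composite will appear at the interim under the full definition; if it were omitted, there would be no shift. This stands as mitigation. But the disclosure neither withholds nor redefines the composite, while the source change and the outputs common to both reports are fixed in the protocol itself.

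It can also be said that Section 8.7.1.1 covers predefined variables, and only in most instances, so items outside the registry need not be read as absent. That is fair. The general rule in Section 8.7, which leaves missing values out of percentages, does not help. With CVD and obesity unavailable for everyone, only patients positive on a registry field could be classified under the full definition, and the percentage would be 100.

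A reader might infer more than the documents support:
- *That every output changes definition.* Age 65+ and prior JAK inhibitor, biologic and immunosuppressant use are plain registry fields and stay stable.
- *That the final report captures all components.* Consent may limit chart access, and Table 5 says only that the items might be in the medical report.
- *That the high-risk dose figure must shift.* Membership changes; the estimate need not.
- *That a rise would show worsening prescribing.* No interim-to-final comparison is planned, and Section 8.9 concedes that the availability of suitable alternatives cannot be reliably assessed. Immobility, clotting disorder and hormone use also fall under caution in Section 6, not under restricted use.

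**Conclusion.** The point holds as a cheap improvement. As planned, the Spanish high-risk proportion is understated at the interim and pushed upward at the final report by the added source. The direction for the proportion follows from Table 5 together with the reading of missing information as absence. The size is unknown: a point or less if the registry already finds nearly all high-risk patients, and 10 to 20 points if it finds only half of a true share of 20% to 40% and charts are complete. Incomplete consent shrinks the shift but leaves the final report mixing chart-abstracted and registry-only patients under one label. The high-risk dosing subgroup changes membership; its dose estimate moves only if chart-only patients are dosed differently or dose data are topped up from charts, and the direction is not fixed. The two ENEIDA entries for long-time smoking contradict each other whatever the size. The SAP may already deal with part of this.

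**What to change.** In Section 8.7, carried into the SAP:

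1. At the ENEIDA interim, report the composite and the high-risk maintenance dose only under a named registry-only definition with its components listed. Do not count unavailable components as absent under the full definition.
2. In the final report, give ENEIDA results under the registry-only definition for all patients, and under the full definition for patients with chart abstraction, stating the number of each. The first gives a like-for-like figure with the interim; the second keeps the two levels of ascertainment apart.
3. In Annex 3 Table 5, reconcile the two ENEIDA entries for long-time smoking, so that it is clear whether smoking belongs to the registry-only composite.

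The cost is one extra column or stratum in the ENEIDA tables and a few lines of text. No new data are needed.

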## 8.2. Setting and Study Population

#### 8.2.1. IBD Registries

#### 8.2.1.1. ENEIDA (ES)

Spain's healthcare system guarantees universal coverage for all residents (N = 47 million) and is principally funded through taxation. Specialist care is provided in specialist care centers and hospitals in the form of outpatient and inpatient care.

Most hospitals in Spain have an electronic medical record (EMR) system that provides access for clinicians to review all care that takes place in the same hospital. Moreover, an increasing number of geographical areas have implemented an EMR system that allows access to all the information generated by public hospitals in the same region. Some also provide access to general practitioner data.

Patients with IBD will typically be followed by their gastroenterologist (specialist) in a hospital outpatient setting on a regular basis. For stable asymptomatic patients, follow-up will be scheduled to happen at least every 2 years, whereas for patients with active moderate to severe UC or with ongoing treatment with biologics, follow-up will happen at least every 6 months, based on clinical guidelines in Spain.

The UC prevalence in Spain has been estimated at around 88 per 100000 population (Marín-Jiménez et al., 2018), the annual incidence at 8.1 per 100000 individuals (Chaparro et al., 2021), which is in line with those reported in other European countries.

As of February 2023, there were 37865 patients with UC enrolled in the ENEIDA registry; between 2000 and 3000 additional patients with UC are enrolled annually in the registry. More than 20000 of the enrolled patients are from centers meeting the criteria for research-quality data. These figures indicate that ENEIDA currently covers about 10% of all existing cases of UC in Spain. However, the registry is likely to enroll a significantly larger proportion of all newly diagnosed patients with UC and of initiators of advanced therapies for UC in Spain.

For specific details on the ENEIDA registry, see Section 8.4.1.

